1 INTRODUCTION

Isavuconazonium sulfate is a new azole antifungal agent that was approved for use in adults for the treatment of invasive aspergillosis (IA) and invasive mucormycosis (IM) in the US and in Europe for treatment of IA; and for the treatment of IM in subjects for whom amphotericin B is inappropriate. These same invasive fungal pathogens are also important hospital-acquired pathogens in critically-ill pediatric subjects, especially those with underlying conditions compromising the immune system and there are currently very limited approved treatment options for pediatric subjects.

Therefore, establishing an efficacious and safe dosage regimen for isavuconazole for use in pediatric subjects will provide important information for physicians treating these subjects.

1.1 Background

As in adults, fungal infections remain an important cause of morbidity and mortality in pediatric subjects. In immunocompromised pediatric subjects, invasive mould infections (IMIs) are a leading cause of mortality [Georgiadou et al, 2012; Al-Rezqi et al, 2009; Burgos et al, 2008; Walsh et al, 2008; Sung & Johnston, 2007; Zaoutis et al, 2006]. In a large prospective multinational study to evaluate the epidemiology and spectrum of IMIs in children, which enrolled 131 pediatric subjects with proven or probable IMIs, the most common diagnosis was IA (75%), followed by other IMIs (17%) and IM (13%) [Wattier et al, 2015]. A large proportion of these subjects had some underlying immunosuppression. Overall mortality was 30% at 12 weeks [Wattier et al, 2015]. Another study identified 48 pediatric subjects with proven or probable IMIs from a retrospective single-center in the US [Georgiadou et al, 2012] and found similar trends with *Aspergillus* species being the most common organism and the majority of subjects being immunocompromised with hematologic malignancy and/or neutropenia. Overall mortality in this study was 31% at 12 weeks; in all subjects, death was attributed to both IMI and the underlying disease.

Invasive Aspergillosis: Risk factors and underlying disease characteristics for IA are comparable between adults and children with the most common being malignancy, such as acute myeloid leukemia (AML) and allogeneic hematopoietic stem cell transplant (HSCT). Chronic granulomatous disease, which is typically diagnosed in children, is also a risk factor [Dornbusch et al, 2009]. The Infectious Diseases Society of America guidelines for the treatment of IA do not distinguish between the disease characteristics in adults and children [Walsh et al, 2008]. Therefore, aside from systemic dosing differences, the treatment guidelines for these 2 populations do not differ.

Invasive Mucormycosis: IM is extremely rare and can occur not only in subjects with a severely compromised immune system, but also occasionally in subjects with traumatic injuries or in subjects with uncontrolled diabetes mellitus. IM is one of the most life-threatening mould infections in subjects with hematologic malignancies and in HSCT recipients [Skiada et al, 2011; Chamilos et al, 2008; Roden et al, 2005]. In a 10-year (1997 to 2006) retrospective study in France, the incidence of IM annually increased with age, from 0.3 per million in children less than 9 years to 3.9 per million subjects > 89 years; overall the

annual incidence was 0.9 per million subjects [Bitar et al, 2009]. The incidence is reportedly 1/10 of the incidence of IA on average [Abidi et al, 2014].

Presentation and pathogenesis of the disease are similar between children and adults. Therefore, diagnosis and treatment recommendations are the same in both populations at risk.

Given the similarity of the pathogenesis and features of invasive fungal infection (IFI) between adults and pediatric subjects for both IA and IM, this IA and IM treatment study in children is designed to assess the safety of the proposed clinical dosage regimen. The proposed clinical dosage regimen is supported by a prior clinical pharmacokinetic and safety study in children. The dosage regimen generates exposures in the pediatric population that are consistent with the exposures achieved in adults receiving the recommended clinical dose for adults. The current pediatric study is intended to evaluate the safety and tolerability of isavuconazonium sulfate in the pediatric population from 1 to < 18 years of age.

1.2 Nonclinical and Clinical Data

An overview of the nonclinical and adult clinical data of isavuconazole can be found in the latest version of the investigator's brochure (IB).

Isavuconazole has been investigated in a phase 1 pharmacokinetic, safety and tolerability study in pediatric subjects following intravenous administration. In this study, a total of 27 pediatric subjects received at least 1 dose of study drug (Protocol 9766-CL-0046). Nine subjects were between 1 and < 6 years of age, 8 subjects were between 6 and < 12 years of age and 10 subjects were between 12 and < 18 years of age. A majority of subjects were white and male. Most subjects had an underlying malignancy. Subjects weighing \leq 40 kg received 10 mg/kg of isavuconazonium sulfate, and subjects > 40 kg received 372 of isavuconazonium sulfate intravenously daily, after a loading regimen.

The vast majority of subjects experienced at least 1 adverse event (AE), and serious adverse events (SAEs) were experienced by about half of all subjects, which is expected given the medical history of the subjects enrolled. About a third of subjects experienced drug-related AEs. Important drug-related events included gastrointestinal (GI) disorders and infusion-related reactions. Two subjects were withdrawn from the study due to an AE. The events leading to withdrawal were increased liver enzymes and QT prolongation, and both events were considered related to study drug. No differences were observed in the AE experience between the 3 age cohorts.

1.3 Summary of Key Safety Information for Study Drugs

In the isavuconazole juvenile toxicity study, the no-observed-adverse-effect-level in rats was determined to be 10 mg/kg per day. In this study, no toxicities were observed in pediatric sensitive organs. A summary of the juvenile toxicity study, as well as an overview of the key isavuconazole safety data collected in adult subjects during the clinical development program can be found in the latest version of the IB.

In addition, isavuconazonium sulfate has been investigated in one pediatric clinical study [Study 9766- CL-0046]. In this small study, important adverse reactions were GI disorders, rash, increased liver enzymes and infusion-related reactions.

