5.1.3 Treatment Compliance

Study drug is administered at the research facility under the supervision of study personnel while the subject remains as an inpatient.

If the subject is discharged while continuing treatment with intravenous dosing, the subject must return to the research facility or other approved location every day to receive the daily intravenous dose. Vital signs will be taken pre and post dose. Infusion reaction and other safety monitoring will be conducted.

Subjects who are discharged from the hospital with oral capsules for at-home administration must return weekly for study drug accountability and to receive new oral dosing supplies. Subjects will be provided with approximately 1-week worth of study medication, dosing instructions and a daily dosing log for documentation of ingestion of the oral study medication.

The subject or parent/legal guardian must record the date and time of oral dosing once the first capsule is ingested. The subject should ingest the entire dose within 5 minutes. If the entire dose is not ingested within 5 minutes, record the reason for dosing delay in the source

documentation. If the subject should vomit any of the medication, this is to be recorded as well. The dose is NOT to be repeated. Compliance of the study drug will be monitored by review of the oral dosing log and the accounting of unused medication returned by the subject at each scheduled visit after day 7 and/or at the EOT visit.

When study drug is administered at the research facility, it will be administered under the supervision of study personnel. A subject daily dosing log will be collected to record date/time and completeness of dosing for each day.

Study subjects and their parents/legal guardians should be counseled on the need to meet 100% compliance with study drug dosing. The investigator or designee should ensure that study subjects adhere to this goal throughout the study.

If compliance is less than 80%, the investigator or designee is to counsel the subject and ensure steps are taken to improve compliance.

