6 DISCONTINUATION

6.1 Discontinuation of Individual Subject(s) From Study Treatment

A discontinuation from treatment is a subject who enrolled in the study and for whom study treatment is permanently discontinued for any reason. The reason for discontinuation from study treatment must be documented in the subject's medical records.

A subject must discontinue study treatment for any of the following reasons:

- Subject requests to stop treatment.
- Any clinical AE, laboratory abnormality or intercurrent illness, in the opinion of the investigator, indicates continued treatment is not in the best interest of the subject.
- Parent(s) or legal guardian withdraws consent.
- Subject experiences a systemic infusion-related reaction (IRR) such as hypotension, dyspnea, chills, dizziness, paresthesia and hypoesthesia attributable to study drug during or shortly after the intravenous administration; however, in case of an infusion-related reaction, the infusion must be stopped immediately and the subject must be discontinued from treatment.

Note: If the IRR signs and symptoms are mild and self-limiting, the subject may continue in the study at the discretion of the investigator.

- Serious hypersensitivity or severe skin reactions, such as anaphylaxis or Stevens Johnson syndrome, have been reported during treatment with other azoles. If subject develops a severe hypersensitivity adverse reaction without alternative etiology, the subject must be discontinued from treatment.
- Investigator's decision that further treatment is not in the best interest of the subject.
- Female subject becomes pregnant.
- Subject is lost to follow-up despite diligent efforts to contact.

Discontinuation of the subject from treatment should be considered if a subject experiences an increase in liver enzymes. For specific liver abnormalities, refer to [Appendix 12.5].

All subjects who discontinue study treatment will remain in the study and should continue to be followed for protocol specific follow-up procedures as outlined in [Table 1 Schedule of Assessments]. The only exception to this is when the subject specifically withdraws consent for any further contact, with him/her or persons previously authorized by the participant to provide this information.

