7.5 Analysis of Safety

7.5.1 Adverse Events

AEs will be coded using MedDRA.

TEAE is defined as an AE observed after starting administration of the study drug through 30 days after the last dose. The number and percentage of subjects with treatment-emergent AEs, SAEs, AEs leading to withdrawal of treatment and AEs related to study drug will be summarized by MedDRA system organ class, MedDRA preferred term for overall subjects and by subjects in each cohort. The number and percentage of AEs by severity will also be summarized. All AEs will be listed.

A study drug-related TEAE is defined as any TEAE with a causal relationship of YES by the investigator.

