6.5.1 Adverse Events

TEAE is defined as an AE observed after starting administration of the study drug through 30 days after EOT. The number and percentage of subjects with treatment-emergent AEs, serious adverse events (SAEs), AEs leading to withdrawal of treatment, and AEs related to study drug will be summarized by MedDRA system organ class, MedDRA High Level term, and MedDRA preferred term for overall subjects and by subjects in each age cohort. The number and percentage of AEs by severity will also be summarized. All AEs will be listed.

A study drug-related TEAE is defined as any TEAE with a causal relationship of YES by the investigator. The incidence of treatment emergent AEs will be summarized by relationship to study drug and severity for all subjects and by each age cohort. The protocol defines how Treatment Emergent AEs are determined. Although all AEs are collected, the summary Table will be based on the TEAEs.

Clinically significant out-of-range laboratory findings are to be determined and documented by the investigator/subinvestigator who is a qualified physician. Clinically significant changes will be recorded as AEs.

An overview table will include the following:

- Number of TEAEs,
- Number and percentage of subjects with TEAEs,
- Number of drug related TEAEs,
- Number and percentage of subjects with drug related TEAEs,
- Number of serious TEAEs,
- Number and percentage of subjects with serious TEAEs,
- Number of serious drug related TEAEs,
- Number and percentage of subjects with serious drug related TEAEs,
- Number of TEAEs leading to permanent discontinuation of study drug,
- Number and percentage of subjects with TEAEs leading to permanent discontinuation of study drug, and
- Number of deaths.

The number and percentage of subjects with TEAEs, as classified by SOC, High Level Term (HLT), and PT will be summarized. Summaries will be provided for the following:

- TEAEs

- drug related TEAEs,
- serious TEAEs,
- drug related serious TEAEs,
- TEAEs leading to permanent discontinuation of study drug,
- drug related TEAEs leading to permanent discontinuation of study drug,

The number and percentage of subjects with TEAEs, as classified by SOC and PT will be summarized by time interval. For each adverse event in a particular interval, a subject will be counted if there is an onset of a treatment-emergent adverse event regardless of onset in other intervals.

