The number and percentage of subjects with TEAEs, as classified by SOC and PT will be summarized by subgroups defined in Section 6.5.7.

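### No recording rule or grouped summary is planned for infusion-related reactions, a named risk, so their incidence may be split across SOC/HLT/PT rows and understated

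*Protocol*

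**What the plan says.** - **Named risk.** Of the earlier paediatric study, Protocol 1.2 says "Important drug-related events included gastrointestinal (GI) disorders and infusion-related reactions". Protocol 1.3 repeats the point: "important adverse reactions were GI disorders, rash, increased liver enzymes and infusion-related reactions". Neither section gives a count.
- **Stopping reason.** Protocol 6.1 lists among the reasons for stopping treatment "Subject experiences a systemic infusion-related reaction (IRR) such as hypotension, dyspnea, chills, dizziness, paresthesia and hypoesthesia attributable to study drug", occurring during or soon after the infusion. A note beneath it adds "If the IRR signs and symptoms are mild and self-limiting, the subject may continue in the study at the discretion of the investigator".
- **Monitoring.** For children discharged on intravenous dosing, Protocol 5.1.3 says "Infusion reaction and other safety monitoring will be conducted". It does not say how a reaction is to be recorded.
- **Tabulation.** Protocol 7.5.1 plans that "AEs leading to withdrawal of treatment and AEs related to study drug will be summarized by MedDRA system organ class, MedDRA preferred term". SAP 6.5.1 adds a level: "The number and percentage of subjects with TEAEs, as classified by SOC, High Level Term (HLT), and PT will be summarized". It also plans an overview, breakdowns by severity, relationship, seriousness, discontinuation and time interval, and a listing of all AEs.
- **Other safety analyses.** SAP 6.5.7 (Other Safety-Related Assessments) contains only the word None. SAP 6.5.3, by contrast, gives the liver risk its own grouped categories and an eDISH plot.

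**The concern.** The six example signs are circulatory (hypotension), respiratory (dyspnea), general (chills) and neurological (dizziness, paresthesia, hypoesthesia). If a site writes down the signs, one child's reaction lands in one or more sign rows, and different children land in different rows. If a site writes a single diagnosis, all such children share one row. The plan does not say which will happen, and sites may differ.

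Safety is a stated objective (Protocol 2.1.1), and Protocol 1.1 describes the study as designed to assess the safety of the dosage regimen. In a study of about 30 children, a reaction affecting several of them could appear as a scatter of one-child rows. A reader of the tables could not tell whether a small row is the whole incidence or a fragment of it.

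**Working it through.** **1. Is there a planned figure to reproduce?** No. The documents give no IRR rate, and the sample size was not formally calculated (SAP 3).

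**2. Does another planned output count children with an IRR?**

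- TEAEs leading to discontinuation (SAP 6.5.1): these miss mild, self-limiting reactions, because the note in Protocol 6.1 lets those children continue.
- TEAEs by time interval: the intervals in SAP 6.9 are study-day windows, not time since infusion. Baseline there ends at the first dose and the next window is Day 2, so an onset after the first dose on Day 1 has no window (SAP Appendix 1 does list a Day 1 visit).
- Vital signs (SAP 6.5.4): these are summarised as values, not cases. SAP 6.9.1 averages continuous values taken on the same day, and the SAP does not say that pre- and post-infusion readings are kept apart. A fall in pressure after an infusion could be diluted.
- Deviation PD2 (SAP 6.2.2): this counts children who met a withdrawal criterion and stayed on. It requires IRRs to be identified child by child, but no rule is given.
- AE listings: an IRR count could be rebuilt from these, but only by a rule chosen after the data are seen.

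**3. How far could the rows understate the incidence?** Inputs: n = 30 (SAP 3); six example signs (Protocol 6.1); 6 affected children, which is an assumption made only for illustration. The exact (Clopper-Pearson) 95% limits for x of n are the 2.5% point of Beta(x, n − x + 1) and the 97.5% point of Beta(x + 1, n − x).

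- One row per child with an IRR: 6/30 = 20.0%, 95% CI 7.7% to 38.6%.
- Each child recorded under one sign, all different: six rows of 1/30 = 3.3%, 95% CI 0.1% to 17.2%. The understatement is 20.0/3.3, about six-fold.
- Every child recorded under one diagnosis term: that row is 6/30 = 20.0%. There is no understatement.

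Between these ends, let each of the 6 children show m of the six signs, drawn at random (20,000 repetitions):

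| Signs per child (m) | Mean count in largest row | Divided by 30 |
|---|---|---|
| 1 | 2.41 | 8.0% |
| 2 | 3.65 | 12.2% |
| 3 | 4.66 | 15.5% |
| 6 | 6.00 | 20.0% |

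**4. Denominator.** The safety analysis set includes every dosed child (SAP 4.3). Route is at the investigator's discretion (Protocol 2.2.1), so some children may never be infused and cannot have an IRR. If 20 or 15 of the 30 were ever infused (assumed), 6 cases would be 6/20 = 30.0% (11.9% to 54.3%) or 6/15 = 40.0% (16.3% to 67.7%).

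**The case against.** The best defence is that nothing need go wrong. If sites enter the diagnosis, the preferred-term row already counts each child once. The eCRF instructions mentioned in Protocol 8.1.4 are not part of these documents and may require exactly that. The study is small and descriptive, all AEs are listed, and infusion start and stop times are documented (Protocol 5.1.1), so a child-by-child review is feasible. All of this stands. It limits the point to a missing prespecification.

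A reader might infer more, and four stronger readings should be resisted.

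- That the incidence will be understated. The documents do not say how the event is recorded, so the understatement runs from none to about six-fold under the assumed 6 of 30. The 3.3% figure is the extreme case.
- That the six signs define an IRR and each comes from a different body system. Protocol 6.1 offers them as examples, and three of the six are neurological. It also requires the reaction to be attributable to study drug. A sign list without that condition would sweep in chills or hypotension from other causes.
- That the trial cannot give the incidence. It could be recovered from the listings, though by a rule set after the fact.
- That severe hypersensitivity has the same problem. Protocol 6.1 names anaphylaxis and Stevens Johnson syndrome as diagnoses, not as sets of signs, and requires discontinuation for a severe hypersensitivity reaction without alternative etiology. Such cases should reach the discontinuation tables, so the split-sign argument does not carry over.

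The defence does not explain why one named risk gets a grouped analysis and this one does not, or what would make a reported IRR rate interpretable if sites word the event differently.

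**Conclusion.** The gap is real but conditional. IRR is a named drug-related risk and a stopping reason, and the plan has neither a recording rule nor a once-per-child summary for it. With an assumed 6 of 30 affected, the largest related row could lie anywhere from 3.3% to 20.0% against a true 20.0%, depending only on how sites word the event. The count of 6 is illustrative. The documents also do not show where MedDRA places each sign; the argument needs only that different signs are different preferred terms. Use of the whole safety analysis set as denominator dilutes the rate further if some children receive only oral drug, however the event is worded. No efficacy endpoint is affected. The point is worth settling before database lock.

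**What to change.** In SAP 6.5.1 or 6.5.7, define one IRR group, fixed before database lock. A child is counted if there is a TEAE that is either:

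- any 'infusion related reaction' term; or
- a preferred term on a list built from the Protocol 6.1 signs, judged by the investigator to be related to study drug, with onset on a day the child received an infusion.

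Use onset clock time only if it is collected: Protocol 7.9 and SAP 6.9.1 mention only AE start and stop dates. On daily intravenous dosing every treatment day is an infusion day, so the relatedness condition does most of the work.

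Count each child once, with an exact 95% CI, for all, serious and leading-to-discontinuation events. Show the result among children who received at least one infusion and in the safety analysis set. No severe hypersensitivity group is needed on this argument.

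If 6.5.7 is used, correct the pointer in SAP 6.5.1 ("classified by SOC and PT will be summarized by subgroups defined in Section 6.5.7"), since the subgroups are in 6.5.8. Separately, the stopping criterion in Protocol 6.1 and its note on mild reactions must be reconciled, because PD2 depends on them; this review takes no view on the clinical rule.

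Cost: one term list and one table, with no new visits or procedures. The grouped rate will look higher than the single-term rows and may include some same-day related signs that are not true IRRs.

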1.4 Risk Benefit Assessment

The safety of isavuconazonium sulfate in pediatric subjects has been investigated in a study with a total of 27 subjects. In this small study, isavuconazonium sulfate appeared to be generally well-tolerated with a safety profile similar to that observed in adults. The efficacy of isavuconazonium sulfate in pediatric subjects has not yet been studied. It is expected that the dosage regimen used in the study will result in efficacious exposures in pediatric subjects and therefore subjects will likely benefit from participating in this study.

Subjects enrolled in this study may experience AEs, including previously unknown AEs related to study drug or may experience procedural complications (e.g., bruising from blood draws and slight skin irritation from the adhesive on the electrocardiogram [ECG] electrodes). While the proposed dosage regimen was established to minimize the number of subjects reaching exposures associated with increased toxicity in adults, some pediatric subjects could reach exposures that resulted in central nervous system and GI-type adverse effects in adults. Subjects with familial short QT syndrome are excluded from participation in this study. Pediatric subjects enrolled in this study will be closely monitored for AEs, especially for liver toxicity. Overall, based on the target population selected for this study, the exclusion criteria and the proposed dosage regimen, which matches adult efficacious exposures, the benefit and risk assessment associated with the participation of pediatric subjects in this clinical study is favorable.

